5.5.1. Primary Outcome and Methodology

The primary efficacy endpoint is the change in UAS7 score from baseline to Week 12 in Period 2, defined as the Week 12 UAS7 score minus the baseline UAS7 score. The analysis of the primary endpoint will consist of treatment comparisons made using analysis of covariance (ANCOVA) controlling for baseline UAS7 score. The ANCOVA model will be based on the mITT population. Missing Week 12 scores will be imputed by carrying forward the participants' baseline scores (BOCF) as described in Section 5.4.

The objective of the primary endpoint is to establish superiority of LY3454738 over placebo.

5.5.2. Secondary and Exploratory Efficacy and Health Outcomes Analyses

The secondary and exploratory efficacy analyses are detailed in Table FRCF.5.1Error! **Reference source not found.** and Table FRCF.5.2. There will be no adjustment for multiple comparisons forother analyses.

5.6. Bioanalytical and Pharmacokinetic/Pharmacodynamic Methods

Pharmacokinetic, Pharmacodynamic and Biomarker analyses to address secondary and exploratory objectives of this study will be described by Lilly in separate PK/PD and Biomarker analysis plans.

5.7. Safety Analyses

The general methods used to summarize safety data, including the definition of baseline value are described in Section 5.3.2.

Safety analyses will include data after rescue, unless otherwise stated, and patients will be analyzed according to the investigational product to which they were randomized at Week 0 (Visit 2). Additional analyses may be conducted using data after rescue to systemic therapy for some safety topics such as systemic treatment-emergent adverse events (TEAEs), and serious adverse events (SAEs). Safety analyses will take place using the safety population defined in Section 5.3.1.

Safety topics that will be addressed include the following: AEs, clinical laboratory evaluations, vital signs and physical characteristics, Columbia Suicide Severity Rating Scale (C-SSRS), the Self-Harm Supplement Form, safety in special groups and circumstances, including adverse events of special interest (AESI) (see Section 5.7.5), and investigational product interruptions.

Unless otherwise specified, by-visit summaries will include planned on-treatment visits. For tables that summarize events (such as AEs, categorical lab abnormalities, shift to maximum value), post-last dose follow-up data will be included. Follow-up data is defined as all data occurring up to 30 days (planned maximum follow-up time) after last dose of treatment including rescue, regardless of study period except for deaths and malignancies. For deaths and malignancies, all available follow-up data up to the end of the study will be included. Listings will include all safety data.

For selected safety assessments, descriptive statistics may be presented for the last measure observed during post-treatment follow-up (up to 30 days after the last dose of treatment including rescue, regardless of study period).

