#### **Intervention Groups and Duration:**

Participants will be randomized in a 3:1 ratio to either Sequence Group 1 or Sequence Group 2:

Sequence Group 1: LY3454738 500 mg IV for 12 weeks followed by placebo for 12 weeks

Sequence Group 2: Placebo for 12 weeks followed by LY3454738 500 mg IV for 12 weeks

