# 9.3. **Populations for Analyses**

Population	Description
Entered	All participants who sign the informed consent form
Modified Intent-to-Treat (mITT)	All participants randomly assigned to study intervention and who take at
	least 1 dose of study intervention. Participants will be analyzed according
	to the intervention to which they were assigned.
Safety	All participants randomly assigned to study intervention and who take at
	least 1 dose of study intervention. Participants will be analyzed according
	to the intervention they actually received within each study period.
Pharmacokinetic (PK) Analysis	All participants randomly assigned to study intervention and who take at
	least 1 dose of study intervention and have PK data available.

The following populations are defined for this study:

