# 9.4. Statistical Analyses

Statistical analysis of this study will be the responsibility of the sponsor or its designee.

Any change to the data analysis methods described in the protocol will require an amendment only if it changes a principal feature of the protocol. Any other change to the data analysis methods described in the protocol, and the justification for making the change, will be described in the statistical analysis plan (SAP) and clinical study report. Additional exploratory analyses of the data will be conducted as deemed appropriate.

The SAP will be finalized prior to unblinding. It will include a more technical and detailed description of the statistical analyses described in this section. This section is a summary of the planned statistical analyses of the most important endpoints including primary and key secondary endpoints.

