#### 9.4.1. General Considerations

Efficacy analyses will be conducted on the Modified Intent-to-Treat (mITT) Population. This set includes all data from all randomized participants receiving at least 1 dose of the IP according to the treatment the participants were assigned.

Safety analyses will be conducted on the Safety Population. This set includes all data from all randomized participants receiving at least 1 dose of the IP according to the treatment the participants actually received.

All tests of treatment effects will be conducted at a 2-sided alpha level of 0.05, unless otherwise stated. All confidence intervals (CIs) will be given at a 2-sided 95% level. Descriptive summaries of continuous data will present the group mean, standard deviation, median, minimum, maximum, and sample size. Descriptive summaries of discrete data will report the number of participants and incidence as a frequency and as a percentage.

The baseline value for Period 2 is defined as the last nonmissing measurement on or before the date of first study drug administration (expected at Week 0). The baseline value for Period 3 is the last available value before the initial dose in Period 3 (expected at Week 12). Other definitions of the baseline value may be used to conduct additional supporting analyses.

A number of efficacy outcome measures are in the form of weekly scores derived from patient daily diary data. For these measures, the weekly score will be derived from the 7 days immediately prior to the study visit. The baseline score will be derived from the 7 days prior to Day 1.

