4.1. Summary of Study Design

Study J1B-MC-FRCF (FRCF) is a multicenter, randomized, double-blind, placebo-controlled, Phase 2 crossover study to evaluate the efficacy and safety of LY3454738 500 mg given intravenously (IV) every 2 weeks (Q2W) versus placebo IV Q2W in adults with CSU inadequately controlled with H₁-antihistamines.

The study duration will be up to approximately 39 weeks over 4 study periods, as shown below:

Period 1: Screening, lasting up to 35 days before Week 0 (Visit 2, baseline)

Period 2: First 12-week treatment, from Week 0 (Day 1) through Week 12:

• Participants will be randomized in a 3:1 ratio to receive either LY3454738 500 mg IV or placebo IV Q2W

Period 3: Second 12-week treatment (crossover), from Week 12 through Week 24:

- Participants who received LY3454738 500 mg IV in Period 2 will receive placebo IV Q2W in Period 3.
- Participants who received placebo IV in Period 2 will receive LY3454738 500 mg IV Q2W in Period 3.

Period 4: Post-treatment follow-up for approximately 10 weeks.

- Participants will not receive study drug in Period 4.
- The last dose of study drug is given at Week 22, which is 6 weeks before the first post-treatment follow-up visit (Visit 801). Thus, participants will have been withdrawn from study drug for a total of 12 weeks at the last post-treatment follow-up visit (Visit 802).

Approximately 85 patients will be screened to achieve approximately 60 randomized participants. A total of approximately 52 evaluable participants are expected.

Throughout the study, participants will take a second-generation H_1 -antihistamine at a dose specified in approved product labeling. Certain participants may receive rescue therapy as described in Section 6.5.2 in the protocol.

Participants who permanently discontinue the study drug early will undergo early termination procedures, including an early termination visit (ETV) and the post-treatment follow-up visits specified in the Schedule of Activities (SoA) (Section 1.3 in the protocol).

Figure FRCF.4.1 illustrates the study design. The blinding procedure is described in the Protocol.

[figure not shown]

Figure FRCF.4.1. Illustration of study design for Clinical Protocol J1B-MC-FRCF.

Abbreviations: C = crossover visit; D = day; Q2W = every 2 weeks; R = randomization visit; W = study week relative to randomization visit; V = visit.

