5.3.1. Analysis Populations

Entered: All participants who sign the informed consent form.

Modified Intent-to-Treat (mITT): All participants randomly assigned to study intervention and who take at least 1 dose of study intervention. Participants will be analyzed according to the intervention to which they were assigned.

Per-Protocol (PPS) population: The PPS populations is defined as all randomized patients who do not commit an Important Protocol Deviation (IPD) that could potentially compromise efficacy results. For more details, patients who missed more than one dose in Period 2 or were enrolled inadvertently will be excluded from Per-Protocol-Set.

Safety: All participants randomly assigned to study intervention and who take at least 1 dose of study intervention. Participants will be analyzed according to the intervention they actually received within each study period.

Pharmacokinetic (PK) Analysis: All participants randomly assigned to study intervention and who take at least 1 dose of study intervention and have PK data available.

Efficacy analyses will be conducted on the Modified Intent-to-Treat (mITT) Population. This set includes all data from all randomized participants receiving at least 1 dose of the IP according to the treatment the participants were assigned.

Safety analyses will be conducted on the Safety Population. This set includes all data from all randomized participants receiving at least 1 dose of the IP according to the treatment the participants actually received.

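### SAP 5.7 groups safety data by the Week 0 product, against the as-received rule it invokes; followed literally, this reverses the Period 3 labels. Separately, the TEAE windows put the first Period 3 infusion in Period 2

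*SAP*

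**What the plan says.** **Grouping.** SAP 5.7 sets the rule for all safety analyses: "patients will be analyzed according to the investigational product to which they were randomized at Week 0 (Visit 2"). Later in the same paragraph it adds: "Safety analyses will take place using the safety population defined in Section 5.3.1". That section, SAP 5.3.1, has a different rule: "Participants will be analyzed according to the intervention they actually received within each study period". Protocol 9.3 assigns the safety population in the same way, "to the intervention they actually received within each study period", and Protocol 9.4.1 analyses safety "according to the treatment the participants actually received". Protocol 9.4 lets the SAP change a method without an amendment unless a principal feature is changed, but the change and "the justification for making the change, will be described in the statistical analysis plan (SAP"). The SAP describes no such change for the safety grouping.

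**Crossover.** The synopsis defines Sequence Group 2 as "Placebo for 12 weeks followed by LY3454738 500 mg IV for 12 weeks", and SAP 4.1 confirms it: "Participants who received placebo IV in Period 2 will receive LY3454738 500 mg IV Q2W in Period 3". Sequence Group 1 takes the reverse order.

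**Period windows.** SAP 5.7.2 counts treatment-emergent adverse events (TEAEs) in Period 2 over V2 to V9 and in Period 3 over V10 to V16. The Schedule of Activities (Protocol 1.3) has an infusion at V9 (Week 12, Day 85) and none at V10. SAP 5.3.2 also expects the first Period 3 dose at Week 12. SAP 5.7.2 uses day and time to sort same-day onsets, but only around the first dose of study treatment.

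**The concern.** In a parallel-group trial, grouping by product randomised and grouping by product received differ only where there are dosing errors. Here they agree in Period 2 and give opposite answers in Period 3 for everyone who continues. The plan intends Period 3 safety output: SAP 5.7.1 summarises exposure in Periods 2 and 3 by treatment group, and SAP 5.7.2 counts TEAEs by period and summarises them by treatment. A programmer who follows SAP 5.7 would head the Period 3 columns with the product that each participant is no longer being given.

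The V9 boundary is a separate defect, and correcting the grouping rule does not cure it. For a placebo-first participant, V9 is the first exposure to LY3454738. Protocol 8.3.7 lists infusion reactions and anaphylaxis as adverse events of special interest, and these can appear on the day of the infusion. The stated windows put such an event in Period 2, where that participant counts as placebo under either grouping rule.

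**Working it through.** The plan gives no figure of its own for this point, so the check is a count from the design.

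**Inputs**
- 60 randomised 3:1 (Protocol 1.1 and 9.2): 45 LY3454738-first, 15 placebo-first.
- Infusions (Schedule of Activities): Period 2 at V2, V4, V5, V6, V7, V8 = 6; Period 3 at V9, V11, V12, V13, V14, V15 = 6.

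**Step 1: labels, all 60 completing**

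| | LY3454738 column | Placebo column |
|---|---|---|
| Period 2, either rule | 45 | 15 |
| Period 3, as received (SAP 5.3.1) | 15 | 45 |
| Period 3, Week 0 product (SAP 5.7) | 45 | 15 |

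Under the Week 0 rule all 60 carry the opposite label in Period 3.

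**Step 2: infusions under the wrong heading**
- LY3454738 shown as placebo: 15 × 6 = 90.
- Placebo shown as LY3454738: 45 × 6 = 270.
- Planned LY3454738 infusions: 45 × 6 + 15 × 6 = 360, and 90/360 = 25%.
- Exposure by the SAP 5.7.1 formula, taken for Period 3 alone: 155 − 85 + 1 = 71 days each, so 15 × 71 = 1,065 LY3454738 participant-days would be reported as placebo.

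Full completion is an upper bound. If only 52 entered and completed Period 3, split 39 and 13, the counts are 13 × 6 = 78 and 39 × 6 = 234. That is an assumption: the documents give 52 as the evaluable number and do not say when the other eight are lost.

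**Step 3: infusions inside the TEAE windows**
- V2 to V9 holds V2, V4, V5, V6, V7, V8 and V9 = 7.
- V10 to V16 holds V11, V12, V13, V14 and V15 = 5.
- A split at the first Period 3 dose would give 6 and 6.

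Of the 60 first LY3454738 infusions, 15 (25%) are given at V9. One same-day reaction among them adds 1/15 = 6.7 points to the Period 2 placebo column.

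**Step 4: onsets between V9 and V10**
- Nominal days strictly between the visits: 86 to 91 = 6.
- With ±3 days at each visit, V9 falls on Days 82 to 88 and V10 on Days 89 to 95. The gap runs from 89 − 88 − 1 = 0 to 95 − 82 − 1 = 12 days.
- Read by visit date, these onsets fall in neither window. If Period 2 runs until V10, they fall in Period 2. If the visit that collects the event decides, they fall in Period 3.

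**Step 5: carryover once the labels are right**
With the half-life of about 2 weeks given in Protocol 4.2 and simple exponential decline, the fraction of the post-dose Week 10 level left after t weeks is 0.5^(t/2): 50% at Week 12, 25% at Week 14, and 0.5^5 = 3% at Week 20. Early Period 3 data in the LY3454738-first group are therefore not pure placebo data.

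**The case against.** **The clause may be a leftover.** SAP 5.7 still lists a suicidality scale that the SAP's revision history says is not available for this study, and SAP 5.7.2 refers to each LY3454738 dose group in a one-dose trial. The same paragraph points to SAP 5.3.1, so a careful programmer might follow that section. This is fair as to intent, and it supports reading the clause as unreconciled text and not as a deliberate change. It does not remove the conflict: the SAP does not say which section governs, and 5.7 is the more specific one.

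**Week 0 grouping can be meaningful.** Participants are randomised to a sequence, Protocol 4.2 uses Period 3 to study safety and durability after LY3454738, and residual drug is present early in Period 3. Columns headed by sequence would mislabel nothing. But SAP 5.7.1 and 5.7.2 head them by treatment. What stands is that sequence should be shown as well.

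**The V9 point is narrower than it may look.** A reader might infer that all events after the V9 infusion go to Period 2. The documents support this clearly only for onsets on the V9 date. Even there, if the collecting visit decides, an onset late on that day first reported at V10 could go to Period 3. A reaction seen and recorded during the post-infusion monitoring at V9 falls in Period 2 on either reading.

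**Pooling.** A reader might also infer that the serious-event, discontinuation, hepatic, renal and registry summaries lose their treatment contrast. That would need those summaries to pool Periods 2 and 3, which the text leaves open. It would also need event risks that the documents do not give, and an assumption of no carryover that fits poorly with the half-life and no washout. SAP 5.7.2 counts TEAEs by period, so pooling does not arise there.

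**Conclusion.** The point holds and should be fixed. SAP 5.7 contradicts the safety population that it invokes and two sections of the protocol. Applied literally, it reverses the treatment label of every continuing participant in the Period 3 exposure and TEAE tables, with up to 90 LY3454738 and 270 placebo infusions under the wrong heading. That size rests on 60 randomised 3:1, full completion, and the SAP 5.7 rule being followed over SAP 5.3.1.

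The V9 boundary error is certain in its infusion count (7 and 5 against 6 and 6). In its effect on events it is limited to same-day onsets, and onsets between V9 and V10 are ambiguous. It matters mainly for the 15 participants whose first LY3454738 infusion is at V9.

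Neither defect reaches the primary efficacy analysis or the power calculation. The Period 2 safety comparison, the main randomised one, is affected only by dosing errors and the V9 boundary. SAP 5.7.2 plans Fisher's exact tests of LY3454738 against placebo without naming a period, so it is not established that any test would use the reversed columns; a test run on Period 3 would.

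**What to change.** 1. Delete the Week 0 clause from SAP 5.7 and let the SAP 5.3.1 rule stand. Label any safety table that covers Period 3 by the treatment received in that period, and show sequence alongside (for example, placebo after LY3454738), so that carryover in the LY3454738-first group stays visible. Barring dosing errors, treatment received and sequence identify the same people within Period 3, so the two labels do not compete.
2. In SAP 5.7.2, end the Period 2 TEAE window just before the first Period 3 dose and start the Period 3 window at that dose. Extend the existing day-and-time rule to the V9 date. This also settles onsets between V9 and V10.

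The cost is one clause, one window definition and the column labels in the table shells. Dose date and time are already recorded (Protocol 6.4). The one extra need is adverse-event onset time on the V9 date, which the documents do not show to be collected for that visit. Where it is missing, the SAP should state a default, for example assignment to Period 3. Separate period displays for every safety summary are not needed to resolve this point.

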5.7.1. Extent of Exposure

Duration of exposure (in days) to study drug will be summarized for the safety population in both Period 2 and 3 by treatment group using descriptive statistics (n, mean, SD, minimum, 1st quartile, median, 3rd quartile, maximum).

For subjects without drug interruption, the duration of exposure for each patient is the date of last dose – date of first dose +1. If subjects have drug interruption, the duration of exposure for each patient is the (Treatment end date before drug interruption – date of first dose +1) + (date of last dose – treatment re-start date +1).

5.7.2. Adverse Events

Adverse events are recorded in the eCRFs. Each AE will be coded to system organ class (SOC) and preferred term (PT) using the Medical Dictionary for Regulatory Activities (MedDRA) version that is current at the time of database lock. Severity of AEs is recorded as mild, moderate, or severe.

A TEAE is defined as an event that either first occurred or worsened in severity after the first dose of study treatment and on or prior to the last visit date during the analysis period. For each event classification term, the number of participants experiencing a TEAE with that classification term will be tabulated. For this study, the TEAEs should be counted by periods: TEAEs for Period 2 for V2-V9; TEAEs for Period 3 for V10-V16; TEAEs for Period 4 after V16.

Treatment-related TEAEs are defined as events that are indicated by the investigator on the eCRF to be related to treatment. For events that are gender specific, the denominator and computation of the percentage will include only participants from the given gender.

Adverse events are classified based upon the MedDRA PT. The MedDRA Lowest Level Term (LLT) will be used in defining which events are treatment-emergent. The maximum severity for each LLT during the baseline period up to first dose of the study medication will be used as baseline. If an event with missing severity is preexisting during the baseline period, and persists during the treatment period, then the baseline severity will be considered mild for determining TEAE (that is, the event is treatment-emergent if the severity is coded moderate or severe postbaseline and not treatment-emergent if the severity is coded mild postbaseline). If an event occurring postbaseline has a missing severity rating, then the event is considered treatment-emergent. The day and time for events where onset is on the day of the first dose of study treatment will both be used to distinguish between pretreatment and posttreatment in order to derive treatment-emergence. Should there be insufficient data for AE start date to make this comparison (for example, the AE start year is the same as the treatment start year, but the AE start month and day are missing), the AE will be considered treatment-emergent.

In an overview table, the number and percentage of subjects who experienced a TEAE or serious adverse event (SAE), died due to an AE, or discontinued from study due to an AE will be summarized by treatment.

The frequency and percentages of patients with TEAEs will be summarized by treatment using MedDRA PT nested within SOC. Events will be ordered by decreasing frequency within SOC. The frequency and percentages of patients with TEAEs by maximum severity will also be summarized by treatment using MedDRA PT nested within SOC.

Fisher's exact test will be performed to compare percentages for each LY3454738 dose group and Placebo at both the SOC and PT levels.

Listings will be presented for all AEs, all SAEs, all AEs leading to death, all AEs leading to study drug temporary interruption, and all AEs leading to discontinuation from the study.

In this study, the following events are being captured as study endpoints and will not be reported as AEs:

- Pruritus (itching)
- Angioedema
- Hives (wheals)

Information on these events will be captured via the UPDD (patient electronic diary).

However, if any of these events is an SAE, the event should be reported as an SAE.

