Receptor occupancy assay		x						x	x						x	x	x	
 
Visit 2: Samples are collected at four time points:
 
1) before infusion starts
 
2) after infusion ends
 
3) 1 hour after infusion ends
 
4) 2 hours after infusion ends.
 
Other visits: Samples are collected before infusion starts.
 

Randomization and	Randomization and Dosing																	
Randomization		Х																
Dosing		Х		х	Х	Х	Х	Х	Х		х	х	х	х	х			

Abbreviations: ADA = anti-drug antibody; AESI = adverse event of special interest; DLQI = Dermatology Life Quality Index; ECG = electrocardiogram; ETV = early termination visit; HBV = hepatitis B virus; HCV = hepatitis C virus; HIV = human immunodeficiency virus; TBNK = T-cells, B-cells, and natural killer (NK) cells; TST = tuberculin skin test; ULN = upper limit of normal; V = visit.

	Post-Tr Follo	eatment w-Up		Comment
	Peri	iod 4	Post-Treatment	
			ETV	
Visit number	V801	V802		
Weeks from randomization	28/	34/		
	ETV+4	ETV+10		
Study day	197	239		
Visit tolerance interval (days)	±7	±7		
Fasting visit				No fasting in this period.
Concomitant medications, including	X	х	X	
medications for indication				
Adverse events	Х	х	Х	For AESIs, additional data are collected.
Vital signs	х	х	Х	Blood pressure, body temperature, pulse rate
Symptom-directed physical examination	Х	х	Х	Includes assessment of skin at every visit (Section 8.2.2)
Patient Diary (Electronic)				
Check electronic diary compliance	Х			The diary is completed daily.
Return electronic diary		х	X	
Patient-Reported Outcomes (Paper)				
DLQI	X	х	Х	
Laboratory Tests and Sample Collections		·		
Hematology	X	х	Х	
Clinical chemistry	X	х	X	
Urine pregnancy	X	х	Х	Only for women of childbearing potential and women with a history of
				tubal ligation; done locally
Pharmacokinetic (PK) samples		X	Х	
Immunogenicity (ADA) samples		X	X	A time-matched PK sample should be collected at each immunogenicity
				sample time point.

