## 4. Study Design

## 4.1. Overall Design

Study J1B-MC-FRCF (FRCF) is a multicenter, randomized, double-blind, placebo-controlled, Phase 2 crossover study to evaluate the efficacy and safety of LY3454738 500 mg given intravenously (IV) every 2 weeks (Q2W) versus placebo IV Q2W in adults with CSU inadequately controlled with H1-antihistamines.

The study duration will be up to approximately 39 weeks over 4 study periods, as shown below:

- Period 1: Screening, lasting up to 35 days before Week 0 (Visit 2, baseline)
- Period 2: First 12-week treatment, from Week 0 (Day 1) through Week 12:
  - Participants will be randomized in a 3:1 ratio to receive either LY3454738 500 mg IV or placebo IV Q2W
- Period 3: Second 12-week treatment (crossover), from Week 12 through Week 24:
  - Participants who received LY3454738 500 mg IV in Period 2 will receive placebo IV Q2W in Period 3.
  - Participants who received placebo IV in Period 2 will receive LY3454738 500 mg IV Q2W in Period 3.

Period 4: Post-treatment follow-up for approximately 10 weeks.

- Participants will not receive study drug in Period 4.
- The last dose of study drug is given at Week 22, which is 6 weeks before the first post-treatment follow-up visit (Visit 801). Thus, participants will have been withdrawn from study drug for a total of 12 weeks at the last post-treatment follow-up visit (Visit 802).

The study schema is presented in Section 1.2.

Throughout the study, participants will take a second-generation  $H_1$ -antihistamine at a dose specified in approved product labeling. Certain participants may receive rescue therapy as described in Section 6.5.2.

Participants who permanently discontinue the study drug early (Section 7.1) will undergo early termination procedures, including an early termination visit (ETV) and the post-treatment follow-up visits specified in the Schedule of Activities (SoA) (Section 1.3).

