## 6.1. Study Interventions Administered

#### Study interventions

This study involves a single dose level of LY3454738 and placebo, as shown below.

Treatment Name	LY3454738	Placebo				
Dosage Formulation	Lyophilized powder	0.9% sodium chloride				
Dosage Level	500 mg	not applicable				
Routes of Administration	IV infusion	IV infusion				
Dosing Instructions	One dose every 2 weeks	One dose every 2 weeks				

Abbreviation: IV = intravenous.

LY3454738 is supplied for clinical trial use as a lyophilized powder formulation in a glass vial. Vials will be supplied in cartons, with the appropriate quantity specific to the planned dispensing schedule of the IPs.

When the IPs are prepared for dosing according to instructions (Section 6.2) it will not be possible to distinguish LY3454738 from placebo.

All participants should be monitored for 30 minutes or longer after dosing, according to investigator practice or local standard of care. Sites must have resuscitation equipment, emergency drugs, and appropriately trained staff available during the infusion and monitoring period, or until completion of all required post-dosing activities (whichever is longer).

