# 8.2. Safety Assessments

#### Visits and order of safety assessments

Safety assessments occur at visits specified in the SoA (Section 1.3). Home or virtual health visits are permitted to assess the safety of the participant under special circumstances (for example, site closure or other restrictions), after consultation with the sponsor's medical monitor. The home or virtual health visits should be documented in the CRF.

If multiple safety assessments are scheduled for the same visit, the preferred order of completion is

- 1) ECG (if applicable) and vital signs first
- 2) other safety assessments, including physical examinations and AE collection, and finally
- 3) blood sample collection for clinical laboratory, PK, pharmacodynamic (PD), pharmacogenetic, biomarker, and immunogenicity testing.

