5.3.2. Definition of Baseline and Postbaseline Measures

The baseline value for Period 2 is defined as the last nonmissing measurement on or before the date of first study drug administration (expected at Week 0). The baseline value for Period 3 is the last available value before the initial dose in Period 3 (expected at Week 12). Other definitions of the baseline value may be used to conduct additional supporting analyses.

A number of efficacy outcome measures are in the form of weekly scores derived from patient daily diary data. For these measures, the weekly score will be derived from the 7 days immediately prior to the study visit. The baseline score will be derived from the 7 days prior to Day 1 (Visit 2) for Period 2, and 7 days prior to Day 85 (Visit 9) for Period 3.

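### The SAP's TEAE windows put Visit 9 in Period 2, but the first crossover infusion is given at Visit 9, so at least the acute reactions to it are counted in the wrong period.

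*SAP*

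**What the plan says.** SAP 5.7.2 counts TEAEs by period: "TEAEs for Period 2 for V2-V9; TEAEs for Period 3 for V10-V16; TEAEs for Period 4 after V16". The TEAE definition in the same section closes with events "on or prior to the last visit date during the analysis period". It has one rule on onset time: "The day and time for events where onset is on the day of the first dose of study treatment will both be used". That rule separates pretreatment from posttreatment events.

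The design puts the crossover elsewhere. Protocol 4.1 runs Period 3 from Week 12 and states: "Participants who received placebo IV in Period 2 will receive LY3454738 500 mg IV Q2W in Period 3". SAP 5.3.2 expects the initial Period 3 dose at Week 12 and takes the Period 3 diary baseline from the week before Day 85 (Visit 9). The dosing row of the Schedule of Activities (Protocol 1.3) is marked at V9 and blank at V10.

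Two rules on the treatment column also differ. SAP 5.3.1 and Protocol 9.3 analyse the safety population by the treatment received in each period. SAP 5.7 invokes that population but analyses patients by the product randomized at Week 0.

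**The concern.** V9 is both the Week 12 endpoint visit for Period 2 and the visit of the first Period 3 infusion, so a visit label cannot separate the two treatments.

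For placebo-first participants, V9 is the first exposure to LY3454738. Protocol 8.3.7 names anaphylaxis and infusion reactions as events of special interest. A same-day reaction to that infusion could be tabulated in the placebo period and be missing from the LY3454738 column of Period 3. For drug-first participants the same rule puts events after the first placebo infusion in the LY3454738 period.

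What can be wrong is the set of TEAE tables by period and treatment, and any Fisher's exact tests run on them.

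**Working it through.** **1. Infusions by period.** Infusion visits in the Schedule of Activities are V2, V4, V5, V6, V7, V8, V9, V11, V12, V13, V14 and V15.

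| Rule | Period 2 infusions | Period 3 infusions |
|---|---|---|
| Design (Period 3 from Day 85) | V2, V4–V8: 6 | V9, V11–V15: 6 |
| SAP 5.7.2 windows | V2, V4–V9: 7 | V11–V15: 5 |

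Protocol 4.2 intends equal treatment durations, which the 6 and 6 split matches.

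**2. Two readings of the windows.** The SAP does not say which applies.

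- *Visit dates.* The phrase "on or prior to the last visit date during the analysis period" favours this reading without settling it. Post-infusion events on the V9 date go to Period 2. The days strictly between V9 and V10 belong to no period: 92 − 85 − 1 = 6 nominal days (Days 86 to 91). With ±3 days at each visit, the gap runs from 89 − 88 − 1 = 0 to 95 − 82 − 1 = 12 days.
- *Collection visits.* Protocol 8.2 prefers ECG and vital signs first, then "other safety assessments, including physical examinations and AE collection, and finally" blood sampling. For receptor occupancy at visits other than Visit 2, which include V9, "Samples are collected before infusion starts". Scheduled AE collection at V9 therefore normally precedes the infusion, and later events are first collected at V10, in Period 3. There is no gap. Events recorded at V9 after the infusion are still misplaced, and Protocol 6.1 creates the occasion: "All participants should be monitored for 30 minutes or longer after dosing".

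The onset-time rule repairs neither reading, because it covers only the first dose of study treatment.

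**3. Size per affected participant.** This assumes tabulation by treatment received. The increases require that the participant does not already have that term in the period that gains the event. The decreases require that the term does not recur in the period that loses it. Denominators are 60 at 3:1 = 45 and 15. The lower bound assumes that only the 52 evaluable participants reach V9, at 3:1 = 39 and 13.

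| Sequence | Period 2 rate | Period 3 rate |
|---|---|---|
| Placebo first | placebo: up to +1/15 = +6.7 points | LY3454738: −1/15 = −6.7 to −1/13 = −7.7 points |
| Drug first | LY3454738: up to +1/45 = +2.2 points | placebo: −1/45 = −2.2 to −1/39 = −2.6 points |

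**4. Illustration on a Fisher test.** The counts are assumed, since the documents give no event rate. When all k events fall in the LY3454738 group of size n₁ out of N, the two-sided p in these cases is C(n₁,k)/C(N,k).

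- 3/15 against 0/45: C(15,3)/C(60,3) = 455/34220 = 0.013.
- One of the three moved to Period 2, leaving 2/15 against 0/45: C(15,2)/C(60,2) = 105/1770 = 0.059.
- With 13 and 39: 286/22100 = 0.013, and 78/1326 = 0.059.

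**5. Carry-over.** The Week 10 dose is on Day 71, so V9 is 85 − 71 = 14 days later. That is about one half-life on the roughly 2 weeks in Protocol 4.2. Protocol 4.3 expects about 90% receptor saturation at the steady-state trough. Attribution for drug-first participants is therefore blurred wherever the boundary is drawn.

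**The case against.** The strongest reply is that the harm depends on the other defect. Under the Week 0 rule in SAP 5.7, a placebo-first participant's V9 reaction appears under placebo wherever the boundary lies. That is correct, and it is why both rules need changing. It does not defend the window, because the Week 0 rule contradicts the safety population that the same paragraph invokes.

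A second reply is that the visit-date reading cannot be intended, since it leaves days in no period, and that the collection-visit reading leaves little error. The reading is indeed open, and the second one is much milder. It still misplaces reactions recorded at V9 after the infusion, which are the acute events of most interest.

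Third, there are safeguards:

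- The SAE table (SAP 5.7.2.1) and the table of AEs leading to discontinuation of study treatment (SAP 5.7.2.2) cover the study drug period rather than these windows.
- Itch, hives and angioedema are not AEs unless serious.
- Event tables take in follow-up to 30 days after the last dose.

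The first two narrow the effect. The third does not say which period an event belongs to. None of them corrects the by-period TEAE tables.

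Finally, Protocol 9.4.5 describes safety as descriptive, SAP 5.7.2 does not say that the Fisher tests are run by period, and the counts above are assumed. This stands: the p-values show sensitivity only and predict nothing.

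**Conclusion.** The window sentence in SAP 5.7.2 is wrong as written. It places the first infusion of the crossed-over treatment in the preceding period, and on either reading at least the acute post-infusion events recorded at V9 are misassigned. On the visit-date reading, all post-infusion events on that date are misassigned and a nominal six-day gap is added.

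Given tabulation by treatment received, one affected participant moves a placebo-first rate by about 7 points and a drug-first rate by about 2 points. The number of affected participants is unknown. The net direction is indeterminate, because the two sequences err in opposite directions and carry-over complicates the larger one. Primary efficacy and the listings, including the hypersensitivity listing in SAP 5.7.6.4, are unaffected.

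The conflict between SAP 5.7 and SAP 5.3.1 is a separate error. If the Week 0 rule stays, Period 3 events remain under the Week 0 product whatever the boundary. Both should be fixed before unblinding.

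**What to change.** Replace the window sentence in SAP 5.7.2 with text to this effect:

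> TEAEs are assigned by onset date and time. Period 2 runs from the start of the first infusion to immediately before the start of the first Period 3 infusion, or to the ETV if none is given. Period 3 runs from the start of the first Period 3 infusion through V16 or the ETV. Period 4 is after V16 or the ETV. The onset day-and-time rule also applies on the date of the first Period 3 infusion.

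Also state:

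- the period for events on that date with no onset time;
- the end of Period 2 for a participant with neither a Period 3 infusion nor an ETV;
- how the 30-day follow-up rule in SAP 5.7 applies to the period tables;
- that an event which emerged in Period 2 and continues unchanged is not recounted in Period 3, and which baseline severity is used to judge worsening after crossover.

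In SAP 5.7, replace the Week 0 rule so that Period 3 events are tabulated under the treatment received in Period 3, consistent with SAP 5.3.1.

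The cost is a few sentences. Dose dates and times are already recorded (Protocol 6.4). The change relies on AE onset times on the V9 date. SAP 5.7.2 already uses onset time on the first-dose day, but the documents do not show that it is collected at V9, so the default for missing times is needed. Only tabulation changes.
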